## 1.0 BACKGROUND AND RATIONALE

Major depressive disorder (MDD) is estimated to currently affect over 280 million individuals around the globe and is now ranked as the leading cause of disability worldwide (1). First-line treatments include pharmacological and psychotherapy. Even though these approaches are effective, a significant proportion of patients are left symptomatic and functionally impaired. Indeed, results from the Sequenced Treatment Alternatives to Relieve Depression Study have shown that after two (2) failed medication trials, remission rates with subsequent trials drop to 10-15% (2). Additionally, up to 50% of patients experience a chronic or recurrent course, and 30 to 40% develop treatment-resistant depression (TRD), having failed to respond to conventional treatments (3). TRD affects about 2% of the population and represents about 30 to 50% of the total treatment cost for MDD (4). Although antidepressants are convenient and simple to administer, discontinuation rates approach 50% after 3 months of use, due to concerns over side effects as much as non-response (5). Finally, intensive psychotherapy programs still achieve only 20-25% remission rates in TRD (6). Novel therapeutic approaches are therefore needed.

Non-invasive brain stimulation (NIBS) techniques, such as transcranial direct current stimulation (tDCS), have been gaining ground in the treatment of various psychiatric disorders. These non-pharmacological approaches possess an advantageous safety and tolerability profile over medication (16). Specific brain regions can be targeted using NIBS approaches, allowing modulation of the underlying dysfunctional brain networks common to various psychiatric conditions.

tDCS is an easy-to-use NIBS technique with a well-established safety and tolerability profile (7)(8) and has been the subject of multiple studies in MDD, with mixed findings (9)(10)(11). It involves the use of small electrodes directly applied to the scalp to stimulate superficial cortical areas (12). tDCS has a well-established safety and tolerability profile and has the advantage to be low-cost, easy-to-use, and portable, with even the potential to do treatments at home (9)(13). So far, some evidence supports the use of tDCS for MDD, with two large randomized controlled trials (RCTs) having been carried out by the same group, with mixed results (14)(15). For example, the landmark tDCS trial by Brunoni et al. (14) (the largest to date) compared the use of tDCS to the antidepressant escitalopram for 10 weeks in a non-inferiority trial (N = 245). Even though participants received escitalopram daily for 10 weeks (70 times overall), only 22 sessions of tDCS were offered during this period. This was in part because tDCS was administered in-clinic during those 10 weeks; the number of sessions therefore had to be limited to maximize attendance and reduce attrition.

This problem could be solved by intensive treatment. Indeed, a recent study by [name]'s group demonstrated that the effect of tDCS could be potentiated if two sessions were administered with a short break in-between, compared to a single session (16). In this study, cortical excitability induced by tDCS lasted only a few minutes when one single session was administered, while becoming prolonged up to more than 24 hours by the administration of two 20 min sessions spaced by 20 min intervals. Our group has also piloted two intensive studies using a similar type of NIBS called transcranial magnetic stimulation (TMS), where we delivered 6 and 8 daily sessions of TMS over a 5-day period. Treatments were safe and well-tolerated, with minimal side effects and dropout rates. Preliminary data also suggested increased clinical effects with more daily sessions. So far, this intensive approach has never been applied to tDCS. This could be due to potential concerns over adverse events (AEs) with such an intensive protocol, although the literature is limited on this issue. A recent review of the literature on the

therapeutic use of tDCS in humans reported no serious AEs over more than 33,200 sessions in N = 1,000 participants who received repeated sessions ( $\leq$  40 min per session,  $\leq$  4 milliamps) (8). The most reported AE is a light rash under the stimulation electrode. Rare cases of mild and temporary skin lesions have also been reported (12)(19); however, this was not associated with any complication (20). In addition, a recent case study where 10 tDCS sessions were administered over 2 days reported only a mild erythema which resolved quickly after the end of stimulation (21). Electrodes improperly soaked in saline can cause skin irritation, but this can be minimized using pre-packaged pre-soaked electrodes with an optimal amount of saline solution. Intensive tDCS protocols could be applied on a large scale given the low-cost, ease-of-use and portability of these devices.

## 2.0 STUDY OBJECTIVES

Primary objective: To assess the safety, tolerability, and feasibility of an intensive tDCS protocol for MDD. We hypothesize that our intensive tDCS protocol will be safe, well-tolerated and feasible.

Secondary objective: To gather preliminary data on the clinical effects of the protocol.

## 3.0 STUDY DESIGN

This will be a prospective, open-label, single-arm feasibility study carried over a 24-month period starting in 2022.

### 3.1 Study population

Participants will be recruited through referrals to our treatment clinic. We will recruit 30 outpatients 18 to 65 years of age with a diagnosis of unipolar MDD according to Diagnostic and Statistical Manual of Mental Disorders, fifth edition (DSM-5) criteria and confirmed by psychiatrists by means of the Mini-International Neuropsychiatric Interview (MINI) with a score of at least 17 on the 17-item Hamilton Depression Rating Scale (HRSD-17) as well as a low risk of suicide (Blumberger et al. 2018). Participants will be required to have had no increase or initiation of any psychotropic medication in the 4 weeks prior to screening and have normal blood work (thyroid, complete blood count, electrolytes) in the past 6 months. Exclusion criteria will be bipolar disorder, substance use disorder within the last 3 months, dementia, personality disorder, brain injury, pregnancy, specific contraindications to tDCS (e.g., intracranial implants) or previous tDCS treatment. Antidepressant use will be permitted, but anticonvulsant medication or benzodiazepine use of more than 2 mg lorazepam equivalent will not be allowed.

### 3.2 Intervention

Treatments will take place over 10 days (Monday to Friday). Participants will receive 5 tDCS sessions each day, for a total of 50 sessions. Each tDCS session will last 20 min at a 2 milliamps intensity and will be spaced by 20 min intervals (3h treatment block). tDCS sessions will be administered through 1x1 tES mini-CT devices (Soterix, New York, USA) already acquired by the clinic (Fig. 1). These devices have been used in several large MDD trials and are Health Canada approved. They are equipped with a "SNAPstrap" fixing system to reliably position the two (2) electrodes (anode and cathode). The electrodes will be placed on the scalp according to the EEG 10-20 system, with the anode in F3 and the cathode in F4. Treatment will be administered by trained research personnel and single-use "SNAPpads" pre-saturated electrodes

will be provided to participants for each treatment. These electrodes contain just the right amount of saline solution to minimize any cutaneous side-effects.

### 3.3 Outcomes

Participants will be initially assessed at baseline one week before treatment, on every treatment day, at the end of the last treatment day, and one and four weeks following treatment. The complete schedule is presented in **Fig. 2-3**.

**Primary objective:** participants will be systematically assessed every day of treatment and at follow-ups for potential AEs, and all AEs will be reported. At each treatment sessions, a safety check (i.e., visual skin examination) will be performed before and after each tDCS session, and pain levels will be assessed using a Verbal Rating Scale (VRS) of 0 to 10 (10 being the maximally tolerable amount of pain) (**Fig. 4**). Cognitive safety will also be assessed pre- and post-treatment using various tests, such as the Rey Auditory Verbal Learning Test, Rey-Osterrieth Complex Figure, Trail Making Test Parts A & B and verbal fluency test (Fig. 3). Completion and retention rates as well as the number of treatment sessions completed will be assessed. The following data will also be collected: number of potential participants referred to the study, number of patients screened, number of potential participants considered eligible, number of participants recruited, number of participants who initiated the intervention, number of treatment sessions completed, dropout rates and number of participants who completed treatment and assessments. Information on attendance in the intervention will also be measured. Regarding the **secondary objective**, depressive symptoms changes will be assessed through the HRSD-17, Montgomery-Asberg Depression Rating Scale (MADRS), Patient Health Questionnaire-9 (PHQ-9) and General Anxiety Disorder-7 (GAD-7) (Fig. 3). We will also use the 6-item HRSD (Fig. 3) before every treatment day and at the end of the last day, which is a highly sensitive depression scale that can be administered daily during treatment (22).

### 3.4 Sample size justification

No single guideline exists for pilot studies sample size calculations, with recommendations varying from 12 participants per group (23), 30 participants per group (24), 10 to 40 participants per group (25)(26) or at least 9% of the main trial's sample size (27). Using the non-central t-distribution approach devised by Julious and Owen (28)(29) and a conservative effect size of 0.5 (30), the required sample size would be of 24 participants. To account for potential dropouts, we choose a sample size of 30 participants.

### 3.5 Statistical analysis

Inferential statistics will be performed on baseline characteristics utilizing independent samples t-tests (two-tailed) for continuous variables and Chi-square tests for categorical variables and to summarise rates of consent, study retention, as well as data quality (completion of outcome measures and missing data). Treatment safety will be assessed by a line listing, frequency tabulations and 95% confidence intervals. We will also perform repeated measures analyses of variance (ANOVA) on mood scales score at different timepoints to assess the effect of the treatment through time. Planned repeated contrasts will be used to make comparisons between the different evaluation times. To evaluate cognitive safety of the treatment in patients, we will use the reliable change index methodology to differentiate the possible effect of the treatment on cognitive functions and outcome results due to practice effects.

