### **3.7 Attendance and Withdrawal Criteria**

Participants will be encouraged to attend all scheduled treatments. Those that do not meet the following criteria will be excluded from the per protocol analysis if they:

- (1) Miss / Fail to attend more than 2 treatment days in the course overall.
- (2) Miss / Fail to attend more than 10 treatment sessions overall.
- (3) Cannot tolerate stimulation
- (4) Change their regimen of psychotropics during the treatment period.
- (5) Withdraw consent to participate.

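### Mood scales: the planned repeated-measures ANOVA has no rule for incomplete series; a mixed model on all observed ratings would be a modest, nearly free improvement to the secondary objective

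*Combined protocol and SAP*

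**What the plan says.** Section 3.5 gives the whole mood analysis in two statements: the team will "perform repeated measures analyses of variance (ANOVA) on mood scales score at different timepoints", and "Planned repeated contrasts will be used to make comparisons between the different evaluation times". Missing data appear in that section only among the items to be summarised, as "data quality (completion of outcome measures and missing data". No available-case rule, imputation, mixed model or sensitivity analysis is given anywhere, and no software is named.

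Several other places bear on how complete the series will be:

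- Section 3.4: "To account for potential dropouts, we choose a sample size of 30 participants", against a stated requirement of 24.
- Section 3.7 removes from the per-protocol analysis those who "Miss / Fail to attend more than 2 treatment days in the course overall", so people who miss 1 or 2 days stay in.
- Section 3.3 schedules the 6-item HRSD "before every treatment day and at the end of the last day", and assessments at baseline, on treatment days, "at the end of the last treatment day, and one and four weeks following treatment".
- Section 3.6 requires an end-of-study assessment when an adverse event ends participation.
- Section 1.0 reports minimal dropout in the group's two earlier intensive TMS pilots.

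The mood scales serve the secondary objective in section 2.0: "To gather preliminary data on the clinical effects of the protocol".

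**The concern.** Classical repeated-measures ANOVA needs a full row of ratings for each participant, so its usual implementation discards, scale by scale, anyone with a gap, including the ratings already collected. The plan foresees two sources of gaps, dropout and missed treatment days, but does not say what the analysis does with them.

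Two things are at stake. The first is precision, in a study of 30. The second is bias: if people who improve less are more likely to leave, the participants who remain make the change look larger than it is. Section 8.0 says a feasible pilot could lead to a large randomised trial, so an inflated mood change could carry forward. A likelihood-based mixed model uses every observed rating and, on complete data, gave the same estimate, standard error and coverage as the complete-case analysis.

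**Working it through.** **Inputs from the documents.** N = 30. There are 10 treatment days (section 3.2), so the 6-item HRSD has 10 + 1 = 11 ratings. For the other scales I assume 4 ratings (baseline, end of treatment, weeks 1 and 4), because the scale-by-visit schedule is in figures not shown. Every missingness rate, SD and correlation below is an assumption; the documents give none.

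**The plan's own figure.** 24 / (1 − 0.20) = 30, so the step from 24 to 30 corresponds to 20% loss, though no rate is stated. The 24 itself cannot be reproduced because alpha, sidedness and power are absent. That is a separate matter and does not enter here.

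**Complete series.** With independent misses at rate q over k ratings, the expected number is 30(1 − q)^k. The clustered figures use a beta-binomial with intraclass correlation 0.3.

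| Ratings | q | Independent | Clustered |
|---|---|---|---|
| 4 | 2% | 30 × 0.98^4 = 27.7 | 28.4 |
| 4 | 5% | 30 × 0.95^4 = 24.4 | 26.2 |
| 11 | 2% | 30 × 0.98^11 = 24.0 | 27.4 |
| 11 | 5% | 30 × 0.95^11 = 17.1 | 23.9 |

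**Precision, four ratings, end-of-treatment change.** The SE ratio of complete cases to available pairs is sqrt(pairs / complete cases).

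- Independent: 1/0.98 = 1.020 and 1/0.95 = 1.053.
- Clustered: sqrt(28.99/28.43) = 1.010 and sqrt(27.50/26.18) = 1.025.
- 20% lost at follow-up: sqrt(30/24) = 1.118.

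For the week-4 change with about 20% random dropout, the precision gain from a mixed model is small: 95% CI width 4.99 against 5.19 at correlation parameter 0.5, and 4.17 against 4.33 at 0.7.

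**Precision, 11 ratings.** If all 11 enter one ANOVA and misses are independent, the complete-case SE of the first-to-last change is 1.12 times (q = 2%) and 1.33 times (q = 5%) that of a mixed model whose covariance is taken as known.

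**Bias, four ratings.** Simulation with n = 30 and 4,000 replicates per cell; means 22/15/15/15.5; SDs 3.5/6/6/6.5; baseline correlation 0.3 or 0.5; post-baseline correlation 0.6 or 0.8. 20% are lost after the end-of-treatment rating, with log-odds linear in the end-of-treatment change. The SD of that change is sqrt(3.5² + 6² − 2r × 3.5 × 6) = 5.97 (r = 0.3) or 5.22 (r = 0.5). Slopes of 0.05 to 0.15 per point therefore give odds ratios from exp(0.05 × 5.22) = 1.30 to exp(0.15 × 5.97) = 2.45 per SD.

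- End of treatment, true −7.0. Complete cases give −6.98 to −7.02 with no dependence, −7.24 to −7.36 at slope 0.05 (bias 0.24 to 0.36), and −7.72 to −7.96 at slope 0.15 (bias 0.72 to 0.96). Available pairs and maximum likelihood are identical: −6.98 to −7.04.
- Week 4, true −6.5, slopes 0.05 to 0.15. Complete cases and available pairs both give −6.64 to −7.33; maximum likelihood gives −6.45 to −6.52.
- Week 4 when loss depends on the week-4 change itself, which is then unseen. Likelihood gives about −6.6 to −7.2 and complete cases about −6.8 to −7.6, so only part of the bias is removed.

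A second set-up (true change −4, SD 4 at baseline and 6 later, about 20% loss linked to a high preceding score) gave a complete-case overstatement of 0.5 to 0.6 points at end of treatment and about 0.25 at week 4. Mixed-model bias was about 0.

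**Bias, 11 ratings.** With 20% dropout during treatment depending on the latest 6-item HRSD change (true first-to-last change −4.0; 400 replicates per cell), complete-case bias is −0.08 to −0.34. Mixed-model bias is −0.03 to +0.02 with a well-fitting AR(1) covariance, and +0.04 to +0.10 with a poorly fitting random-slope covariance.

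**The case against.** Repeated-measures ANOVA is a recognised method, and no passage contradicts it. The outcome is secondary and preliminary, in an open-label single-arm feasibility study. No decision rule uses it, and completion will be reported, so attrition would be visible. The largest end-of-treatment bias above (0.96 points) is no larger than the sampling SD of the estimate, about 1.0 to 1.25. No model supplies the missing control for placebo response or regression to the mean. Loss may be low: the TMS pilots had minimal dropout (indirect evidence, from 5-day courses), section 4.1 selects people able to keep to the schedule, and the section 3.6 end-of-study assessment may add a rating after withdrawal for an adverse event. All of this stands, and it keeps the point modest. None of it supplies a handling rule, one extra rating does not complete a series, and reporting attrition does not correct an estimate.

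A reader might infer more than the documents support:

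- That the plan says it will delete incomplete participants. It does not; that is the method's usual behaviour.
- That about 17 of 30 would be analysed. This needs all 11 ratings in one ANOVA, 5% missed per rating and independence. The text does not say that all 11 enter one ANOVA or whether missed days are made up, and clustering alone raises the figure to 23.9.
- That 20% is the expected dropout, or 2 missed days the expected pattern. The first is only arithmetic from 24 and 30; the second is an exclusion limit.
- That a bias near 1 point is likely. An odds ratio of 2.45 per SD is strong dependence: those lost improve about 3.2 points and completers about 8.0.
- That a mixed model removes bias in general. It does so only if loss depends on observed ratings.

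**Conclusion.** The point holds as a worthwhile, low-cost improvement rather than an error that undermines the study. The named analysis gives no way to use incomplete series, although the plan itself makes them foreseeable.

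On assumed missingness, the four-visit precision loss is about 1% to 5%, or about 12% at 20% loss. Complete-case bias at end of treatment is nil if loss is unrelated to response, about 0.25 to 0.4 points under mild dependence, and up to about 1 point under strong dependence. For that change, a paired analysis of everyone with both ratings does as well, provided the end-of-treatment rating is observed. The mixed model adds most at week 4, where pairs are biased too, and in the daily series. The primary safety, tolerability and feasibility objective is unaffected.

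**What to change.** In section 3.5, replace the ANOVA with a likelihood-based linear mixed model for each mood scale:

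- time as a categorical factor;
- all observed ratings from everyone who started treatment;
- the missing-at-random assumption stated;
- small-sample degrees of freedom;
- the covariance structure named in advance. Unstructured is feasible for 4 ratings (4 × 5 / 2 = 10 parameters) but not sensible for 11 (11 × 12 / 2 = 66 parameters with 30 participants). A parsimonious form such as AR(1), with or without a random intercept, suits the 6-item HRSD.

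Report changes from baseline with 95% confidence intervals. If the ANOVA is kept, the minimum is to state how incomplete series are handled and to report the paired change in everyone with both ratings. That covers end of treatment but not week 4.

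The cost is SAP wording and a standard procedure, with no extra participants, visits or data. The downsides are reliance on missing at random, only partial bias removal if loss depends on unobserved scores, and a covariance choice in a small sample (a poor one left up to 0.10 points of bias in the 11-rating simulation). The model adds little for participants with only a baseline rating.

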### 3.6 Safety and adverse events

Hundreds of thousands of people have received tDCS over the last 25 years. Data available shows that tDCS is a very safe treatment with little or no side effects ((7), (8)). A recent review of the literature on the therapeutic use of tDCS in humans reported no serious AE over more than 33,200 sessions in N = 1,000 participants who received repeated sessions ( $\leq$  40 min per session,  $\leq$  4 milliamps) (8). The most common of the reported side effects is simply a mild and temporary skin lesion under the electrode. A systematic review of 209 tDCS studies reported as side effects: itching (active treatment vs. placebo: 39.3% vs. 32.9%), tingling (22.2% vs. 18.3%), headache (14.8% vs. 16.2%), burning sensation (8.7% vs. 10.0%) and discomfort (10.4% vs. 13.4%) (31). Rare cases of mild and temporary skin lesions have also been reported (19), (12); however, the literature is reassuring to this effect (20). **In addition, a recent case study where 10 tDCS sessions were administered over 2 days reported only a mild erythema which resolved quickly after the end of stimulation (21). Rare cases of skin burn under the electrodes have been reported. These cases were usually associated with incorrect application of the electrode or evaporation of the contact medium.** Most burns were superficial and healed without scarring. As previously stated, the use of single-use "SNAPPads" pre-saturated electrodes and application by trained personnel greatly minimizes the risk of skin reaction. Across the literature, only 11 cases of manic or hypomanic switches have been reported in bipolar patients, and it is not clear that these were actually related to tDCS. tDCS has never been shown to cause cerebral edema or changes in the blood-brain barrier. tDCS causes negligible temperature changes in the skin, making thermal damage to the brain very unlikely. Electrodes improperly soaked in saline can cause skin irritation, but this can be minimized by the use of bagged electrodes pre-soaked with the optimum amount of solution such as we will use in this study. In addition, reliable data from patients who received 100 to 1000 sessions of tDCS indicate no adverse effects due to cumulative exposure. Finally, no seizures were reported in association with the use of tDCS.

Considering that very little data is available regarding intensive tDCS treatments, participants will be monitored by a dermatologist. An initial consultation will take place before the start of the treatment (Visite 2) and patients will be reassessed at the end of treatment session (visite 13). During the treatment week, high-resolution photographs of the skin will be taken daily before and after treatments and shared with the dermatologist, who will assess the treatment sites for skin lesions using a a global rating scale (0:absent to 3: severe). The dermatologist will advise the treatment team to continue or to stop treatment.

Common side effects are expected and will be recorded separately from AEs. Participants will be asked to defer any medication changes for 4 weeks before and during the course of treatment to avoid confounding effects. All AEs reported during the study will be recorded in patients' research file and include the following information: description and nature of event, onset time and date, duration, intensity, seriousness, relationship to treatment, action taken and evolution. In case of a serious adverse event, the aforementioned information will be collected in detail and will be reported to the CHUM IRB. Any AEs deemed to be related to the study by the Primary Investigator (PI), or that result in a participant's withdrawal from the study, will be followed until its resolution or until the patient is considered stable. The decision as to whether or not an AE is sufficiently severe to warrant the termination of patient treatment will be left to the clinical judgment of the (PI). A participant may also voluntarily withdraw from treatment due to what he/she perceives as an intolerable AE. If either of these occurs, the participant will be required to undergo an end-of-study assessment and will be offered appropriate care under medical supervision until the condition becomes stable.

Procedures have been developed for researchers-developers and research staff involved in managing adverse incidents. One objective of these procedures is to describe the various processes surrounding management, documentation and tracking of serious or minor adverse effects that may arise during and after a clinical trial with or without a research product. They also define any reporting requirements that apply to the developer, regulatory bodies and Research Ethics Committee (REC). All serious AEs will be reported punctually to the CHUM's Institutional Review Board. In the event of a SAE or UP, the PI implement the following procedures:

1. When the study coordinator and/or PI become aware of a serious AE, reporting must be implemented in a timely manner
2. The study coordinator will complete the required Quebec-government "Adverse Event Reporting Form" and submit the form to the PI.
3. The event will be reviewed to determine whether it is a SAE or an AE.
4. The serious AE form will then be submitted to the CHUM Institutional Review Board regarding these deadlines

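### Does recording common side effects apart from adverse events leave a hole in the safety analysis?

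*Combined protocol and SAP*

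**What the plan says.** The primary objective in section 2.0 is "To assess the safety, tolerability, and feasibility of an intensive tDCS protocol for MDD". Section 3.2 sets the exposure: "Participants will receive 5 tDCS sessions each day, for a total of 50 sessions".

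For that objective, section 3.3 says that "participants will be systematically assessed every day of treatment and at follow-ups for potential AEs, and all AEs will be reported". It adds a skin check before and after each session, cognitive testing before and after treatment, and a pain rating: "pain levels will be assessed using a Verbal Rating Scale (VRS) of 0 to 10".

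Section 3.6 deals with the records. It says "Common side effects are expected and will be recorded separately from AEs", and for AEs "All AEs reported during the study will be recorded in patients' research file and include the following information", followed by eight items. AEs that are judged related, or that lead to withdrawal, are followed until they resolve or the participant is stable. The same section first summarises the literature ("A systematic review of 209 tDCS studies reported as side effects: itching", then tingling, headache, burning sensation and discomfort). It later refers to procedures for documenting both serious and minor adverse effects.

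The whole safety analysis in section 3.5 is one sentence: "Treatment safety will be assessed by a line listing, frequency tabulations and 95% confidence intervals".

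**The concern.** Three things are absent from the visible text:

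- Section 3.6 does not say that its common side effects are the ones in its own literature summary.
- It gives no rule for when a side effect is also an AE. The only classification step described is serious versus non-serious.
- Section 3.5 does not say that the side-effect record is tabulated.

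The label has consequences. An AE carries eight recorded items, possible follow-up and a promise of reporting, and nothing equivalent is written for the other record. Two staff members could file the same itching or headache differently, so an AE count and its confidence interval would depend partly on who recorded it. In a single-arm study of a little-tested schedule, mild and frequent effects are much of what tolerability means. If they sat in a record nobody analysed, the primary result would look better than the experience of the participants.

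**Working it through.** The plan states no figure on this point, so there is none to reproduce. The check is a comparison of sections, followed by an illustration of size.

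**1. Does section 3.5 treat the two records differently?** The term AE occurs 0 times in section 3.5, and side effect occurs 0 times. The section names no source record at all. Its subject is treatment safety, which covers both. Reading it as covering AEs only would assign to AEs an analysis that the text does not assign to them. Section 3.3 does mention AEs (twice) and not side effects, but it says nothing that limits the tables in section 3.5.

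**2. Which effects depend on the label?** Section 3.6 takes five effects from the systematic review.

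| Effect | Measured whatever the label? |
|---|---|
| Headache, burning sensation, discomfort (3) | On the 0 to 10 scale, so far as they are rated as pain |
| Itching, tingling (5 − 3 = 2) | No named intensity measure |
| Skin reaction (outside the five) | Check before and after each session; daily photographs; dermatologist's rating from 0 to 3 |

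The exposed part is mainly mild itching and tingling, and headache if it is not rated as pain. Effects that stop treatment have their own routes: section 3.6 follows AEs that lead to withdrawal, and section 3.7 lists inability to tolerate stimulation among its criteria.

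**3. How large could the difference be?** Inputs are n = 30 (section 3.4) and an itching figure of 39.3% under active treatment (section 3.6). Section 3.6 does not say whether that percentage is of participants, and it does not come from this schedule, so this is an illustration and not a forecast.

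- Expected count: 30 × 0.393 = 11.79, about 12.
- If tabulated: 12/30 = 40%, exact (Clopper-Pearson) 95% CI 22.7% to 59.4%.
- If no case appears in the AE table and the other record is not tabulated: 0/30, upper limit 1 − 0.025^(1/30) = 11.6%.

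The second table needs two conditions together: every case filed as a side effect only, and the side-effect record left out of the analysis. The plan states neither.

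**4. What if staff label inconsistently?** Suppose k of the 12 participants with itching are filed under AEs and the other 12 − k under side effects. With both records tabulated, the combined count is k + (12 − k) = 12 for every k. Labelling moves cases between two columns and does not lose them. Only an AE-only count would vary, and no threshold or go/no-go rule in the plan uses one.

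**5. Would extra data collection help?** A daily intensity entry for the expected effects would add up to 30 × 10 = 300 entries over the treatment days. The gap lies in definition and presentation, and those entries would close neither.

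**The case for a change.** The strongest point on the other side is that the protocol uses the two words loosely. Section 1.0 names a light rash under the electrode as the AE reported most often. Section 3.6 names a mild skin lesion in the same place as the commonest side effect. If the authors put similar reactions under both labels, staff may do so too. Inferring that the literature list defines the expected effects would still not say when one of them becomes an AE. Confirming in a sentence that both records are tabulated would also cost little.

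The factual part stands: the visible text has no express list and no boundary between side effect and AE. The inference is weaker. The looseness is clearest for skin reactions, and these are examined, photographed and graded independently of the label. A list or session form may also exist where it cannot be seen here. Fig. 4, cited in section 3.3 alongside the skin check and pain rating, is not shown, and the procedures mentioned in section 3.6 are not reproduced. The absence of a form from the visible text is therefore not evidence that the trial lacks one. Recording expected effects separately is a legitimate choice, and the text does not exclude them from analysis.

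**Conclusion.** No change to the plan follows. It leaves a detail unstated, and analysts following it as written would fill it sensibly by listing and tabulating both records under treatment safety. On that reading the safety conclusion is sound, and inconsistent labelling shifts cases between columns without changing the combined count. What remains is possible variation in an AE-only count for mild, non-limiting itching, tingling or headache, on which no decision rule depends. The contrast between 0 of 30 and 12 of 30 is the extreme case. It requires the side-effect record to go unanalysed, and it borrows a literature percentage for an untested schedule.

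This conclusion assumes that both records are kept, as section 3.6 says, and that treatment safety in section 3.5 has its ordinary broad meaning. A cross-reference to the list or form in use, and a note that both records are tabulated, would be optional tidying. Reporting of serious events is not shown to be affected.
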